3.2.3. Noninferiority Margin

In a historical study ([Beck et al 2014](#)), the difference of percentage change from baseline to Day 29 in EASI scores between active control (placebo and glucocorticoids) and placebo was 27.1% with the derived lower limit of 95% CI 16.4%. Therefore, 27% constitutes the minimum expected benefit of triamcinolone (active control) over vehicle. Given that the result is based on 2 studies with small sample sizes, the margin is chosen to be -10%, which is between a half of the lower 95% CI (-8%) and 50% of the minimum effect (-13.5%).

Noninferiority analysis will be performed between each of the active treatment groups and triamcinolone.

3.3. Sample Size Considerations

In order to provide a large safety database and to provided adequate power for efficacy variables, the total sample size for the study is 300 subjects randomized at a 1:1:1:1:1:1 ratio (stratified by baseline EASI score) to treatment with INCB018424 1.5% BID, INCB018424 1.5% QD, INCB018424 0.5% QD, INCB018424 0.15% QD, triamcinolone (active control), and vehicle.

3.4. Schedule of Assessments

Refer to Protocol dated 15 SEP 2016 for a full description of all study procedures and assessment schedules for this study.

4. DATA HANDLING DEFINITIONS AND CONVENTIONS

4.1. Scheduled Study Evaluations and Study Periods

4.1.1. Definitions for Day 1, Baseline, and the Last Available Value

Day 1, baseline, and last available value for the DB period and the open-label period are defined in [Table 1](#).

Table 1: Definition of Day 1, Baseline, and Last Available Value

Study Period	Treatment Group	Day 1	Baseline	Last Available Value
DB period	INCB018424 cream 1.5% BID 1.5% QD 0.5% QD 0.15% QD Vehicle triamcinolone	Date of first application or date of randomization for subjects randomized but not treated in the DB period	The last nonmissing measurement obtained on or before the day of the first dose.	The last nonmissing measurement obtained after the first dose, and within 30 days after the last dose in the DB period or before the first dose in the extension period, whichever is earlier.
Open-label period	INCB018424 cream 1.5% BID	Date of first application in DB period	The last nonmissing measurement obtained on or before the day of the first dose in DB period	The last nonmissing measurement obtained after the first dose and within 30 days after the last dose.
	INCB018424 cream 1.5% QD 0.5% QD 0.15% QD Vehicle triamcinolone	Date of first application in open-label period	The last nonmissing measurement obtained on or before the day of the first dose in the open-label period	The last nonmissing measurement obtained after the first dose in open-label period and within 30 days after the last dose.

When scheduled assessments and unscheduled assessments occur on the same day and time of the assessment or when the first dose is not available, use the following convention to determine the baseline value:

- If both a scheduled and an unscheduled visit are available on the day of the first dose and the time is missing, use the scheduled assessment as baseline.
- If all scheduled assessments are missing on the day of the first dose and an unscheduled assessment is available, use the unscheduled assessment as baseline.

4.1.2. Study Day

Study Day 1 is used to calculate the study day for mapping scheduled visits. Study Day 1 is the date of the first dose of INCB018424 cream, vehicle, or triamcinolone cream in the DB treatment period.

If a visit/reporting date is on or after Study Day 1, then the study day at the visit/reporting date will be calculated as

$$\text{Study Day \#} = (\text{Visit/Reporting Date} - \text{Study Day 1 date} + 1).$$

If the visit/reporting date is before Day 1, then the study day at the visit/reporting date will be calculated as

Study Day # = (Visit/Reporting Date – Study Day 1 date).

A study day of -1 indicates 1 day before Study Day 1.

4.2. Variable Definitions

4.2.1. Age

Subject age will be calculated as the integer part of the number of years from date of birth to the date of signing the informed consent form, using the following formula:

Age = integer part of (date of informed consent – date of birth + 1) / 365.25

4.2.2. Body Mass Index

Body mass index will be calculated as follows:

BMI (kg/m²) = [weight (kg)] / [height (m)]²

4.2.3. Prior and Concomitant Medication

Prior medication is defined as any nonstudy medication started before the first application of study treatment.

Concomitant medication is defined as any nonstudy medication that is started accordingly:

- Before the date of first application of study treatment and is ongoing throughout the study or ends on/after the first application of study treatment.
- On/after the date of first application of study treatment and is ongoing or ends during the course of study treatment.

A prior medication could also be classified as "both prior and concomitant medication" if the end date is on or after the first application of study treatment. In the listing, it will be indicated whether a medication is prior-only, concomitant-only, or both prior and concomitant.

For the purposes of analysis, all medications will be considered concomitant medications unless the medications can unequivocally be defined as not concomitant.

5. STATISTICAL METHODOLOGY

5.1. General Methodology

Unless otherwise noted, SAS® software (SAS Institute Inc, Cary, NC; Version 9 or later) will be used for the generation of all tables, graphs, and statistical analyses. Descriptive summaries for continuous variables will include, but not be limited to, the number of observations, mean, standard deviation, median, minimum, and maximum. Descriptive summaries for categorical variables will include the number and percentage of subjects in each category.

During the DB period, the safety population will be used for all safety analyses, and the ITT population will be used for all efficacy analyses. [REDACTED]

Interim analyses are planned for this Protocol as defined in [Section 9](#).

5.2. Treatment Groups

This is a study in subjects with AD, with a DB, randomized, and vehicle- and active (triamcinolone 0.1% cream)-controlled treatment period followed by an optional open-label treatment period. Data will be summarized based on the treatment regimen that was initially assigned or that subjects received during the DB period.

- DB period versus open-label period:
 - INCB018424 1.5% BID
 - INCB018424 1.5% QD
 - INCB018424 0.5% QD
 - INCB018424 0.15% QD
 - TAC*
 - Vehicle BID

*Active control (triamcinolone 0.1% cream) BID for 4 weeks followed by vehicle cream BID for 4 weeks.

Table summaries, unless otherwise indicated, will present data by treatment group. The results will be summarized and presented separately for the DB period and open-label period.

5.3. Analysis Populations

5.3.1. Double-Blind Period

5.3.1.1. Intent-to-Treat Population

[figure not shown]
All subjects who are randomized to the study constitute the ITT population in the DB period. Treatment groups for this population will be defined according to the treatment assignment at the time of randomization regardless of the actual study treatment the subject might receive during study participation. This population will be used for analyses of all efficacy data in the DB Treatment Period.

5.3.1.2. Per-Protocol Population

Subjects in the ITT population who are considered to be sufficiently compliant with the Protocol compose the PP population, which is defined for supportive sensitivity analyses for efficacy endpoints in the treatment period.

5.3.1.3. Safety Population

The safety population in the DB treatment period includes all enrolled subjects who applied at least 1 dose of INCB018424 cream, triamcinolone cream, or vehicle cream. Treatment groups for this population will be determined according to the actual treatment the subject received regardless of assigned study treatment. All safety analyses will be conducted using the safety population.

5.3.2. Open-Label Period

All analyses for the open-label period will be conducted with the open-label evaluable population, which includes all subjects who applied at least 1 dose of INCB018424 1.5% cream during the open-label period.

6. BASELINE, EXPOSURE, AND DISPOSITION VARIABLES AND ANALYSES

6.1. Baseline and Demographics, Physical Characteristics, and Disease History

The following demographic variables will be summarized for the ITT population in the DB period, and open-label evaluable population in the open-label period: age, sex, race, ethnicity, weight, height, BMI.

The following baseline disease characteristics will be summarized for the ITT population:

- Months since first onset of AD
- Prior history of asthma (No/Yes)
- Prior allergies (food, environmental) (No/Yes)
- History of contact dermatitis (No/Yes)
- Common complications of AD
- Prior treatments for AD
- Months since onset of current AD
- Prior therapy for AD given in the past 30 days (No/Yes)
- Total BSA involvement in current AD episode
- Facial involvement (No/Yes)
- Number of AD episodes/flare-ups over the last 12 months

6.2. Disposition of Subjects

The number and percentage of subjects who were treated, randomized, and completed the DB treatment period through Week 4 and Week 8; were treated in open-label period; completed the open-label period; discontinued from the study or study treatment during the DB period; and discontinued from the study during the open-label period with a primary reason for discontinuation will be summarized for the ITT population in the DB period and open-label evaluable population in open-label period.

6.3. Protocol Deviations and Violations

Protocol deviations and violations recorded in the eCRF will be presented in the subject data listings.

6.4. Exposure

For subjects in the safety population in the DB period and in the open-label evaluable population in the open-label period, descriptive statistics will be provided by treatment group for duration of treatment, average daily dose, and total dose. Duration of treatment with INCB018424 cream, vehicle cream, or triamcinolone cream is defined as the number of days from Day 1 to the last record (defined in [Table 2](#)) of INCB018424 cream, vehicle cream, or triamcinolone cream application.

Table 2: Duration of Treatment

Study Period	Treatment Group	Day 1	Last Record
DB period	All treatment groups	Date of first application in the DB period	Date of last record in the DB period
	INCB018424 cream 1.5% BID	Date of first application in the DB Period	Date of last record in the open-label period
Open-label period	INCB018424 cream 1.5% QD 0.5% QD 0.15% QD Vehicle triamcinolone	Date of first application in the open-label period	Date of last record in the open-label period

6.5. Study Drug Compliance

Overall compliance (%) for the application of INCB018424 cream, vehicle cream, or triamcinolone cream (4 weeks) followed by vehicle cream (4 weeks) will be calculated for all subjects in the safety (DB period) and open-label evaluable (open-label period) populations as follows:

$$\text{Overall compliance (\%)} = 100 \times [\text{total amount dispensed} - \text{total amount returned}] / [\text{intended "dose"}]$$

- Total amount dispensed is defined as the sum of the weights of tubes dispensed before the current visit.
- Total amount returned is defined as the sum of the weights of the tubes returned before and at the current visit.
- The intended dose will be based on the earliest study day of permanent discontinuation of study drug (ie, first AE with action taken = "drug withdrawn" for AE discontinuation) or last study drug record in the database.

6.6. Medical History

For subjects in the ITT population in the DB period, medical history will be summarized by assigned treatment groups. This summary will include the number and percentage of subjects with medical history for each body system/organ class as documented in the eCRF.

6.7. Prior and Concomitant Medication

For subjects in the safety population in the DB period and the open-label evaluable population in the open-label period, prior medications and concomitant medications will be coded using the WHO Drug Dictionary and summarized by WHO drug class and WHO drug term. Results will be summarized as number and percentage of subjects with prior and concomitant medications by PT and WHO drug class.

Prior medication information for AD will also be used to identify medication received by subjects before enrollment into the study in the treatment periods. Prior medications for AD will be summarized by treatment group as well as listed.

7. EFFICACY

7.1. General Considerations

For continuous measurements, summary statistics will include sample size, mean, median, standard deviation, standard error of the mean, minimum, and maximum. For all continuous variables, both the actual value and change and/or percentage from baseline (if available) will be analyzed.

For categorical measurements, summary statistics will include sample size, frequency, and percentages.

All by-visit analyses will include the follow-up period if the data are available.

7.1.1. Handling of Dropouts or Missing Data

In general, for continuous endpoints on primary and secondary endpoints, any subject who discontinues from the study before the timepoint of interest may have missing data imputed using the imputation techniques, such as MMRM under the missing-at-random assumption. MMRM model implicitly adjusts for missing data through a variance-covariance structure.

For response endpoints, all nonresponders, as well as all subjects who discontinue study treatment at any time before the timepoint of interest or discontinue from the study for any reason, will be defined as nonresponders for the NRI analysis.

For other endpoints, missing observations will be handled as detailed in the specific sections addressing each analysis.

7.2. Efficacy Measures

7.2.1. Primary Efficacy Measures

Atopic dermatitis will be assessed using the EASI scoring system, which is a validated disease measurement for clinical studies ([Hanifin et al 2001](#)). The severity strata for the EASI are as follows: 0 = clear; 0.1 to 1.0 = almost clear; 1.1 to 7.0 = mild; 7.1 to 21.0 = moderate; 21.1 to 50.0 = severe; and 50.1 to 72.0 = very severe ([Leshem et al 2015](#)).

The EASI score ([Table 3](#)) examines 4 areas of the body and weights them for subjects 8 years of age and older as follows:

Head/Neck (H) = 0.1, Upper limbs (UL) = 0.2, Trunk (T) = 0.3, and Lower limbs (LL) = 0.4.

The percentage of area involved for each of the 4 body regions is weighted as follows: 0 = no eruption, 1 = some to < 10%, 2 = 10% to 29%, 3 = 30% to 49%, 4 = 50% to 69%, 5 = 70% to 89%, and 6 = 90% to 100%.

Each of the 4 body regions is assessed separately for erythema (E), induration/papulation/edema (I), excoriations (Ex), and lichenification (L) for an average degree of severity of each sign in each region with: 0 = none, 1 = mild, 2 = moderate, and 3 = severe, with half-step allowed.

Table 3: EASI Score Calculation

Body Region	EASI Score
Head/Neck (H)	$(E + I + Ex + L) \times \text{Area score} \times 0.1$
Upper limbs (UL)	$(E + I + Ex + L) \times \text{Area score} \times 0.2$
Trunk (T)	$(E + I + Ex + L) \times \text{Area score} \times 0.3$
Lower limbs (LL)	$(E + I + Ex + L) \times \text{Area score} \times 0.4$
EASI total	Sum of the above 4 body region scores

Missing values will not be imputed. An EASI total score is calculated as the sum of the nonmissing scores and will only be calculated when all subscores are nonmissing.

The PI in EASI score from baseline will be computed as follows:

$$\text{PI} = 100 \times (\text{baseline EASI score} - \text{observed EASI score}) / \text{baseline EASI score}$$

A positive score denotes improvement, and a negative score denotes worsening.

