3.1. Subject Inclusion Criteria

A subject who meets all of the following criteria may be included in the study:

1. Adult men and women aged 18 to 70 years, inclusive.
2. Subjects diagnosed with AD as defined by the Hanifin and Rajka ([1980](#)) criteria.
3. Subjects with a history of AD for at least 2 years.
4. Subjects with an IGA score of 2 to 3 at screening and baseline.
5. Subjects with BSA of AD involvement, excluding the face and intertriginous areas, of 3% to 20% at screening and baseline.
6. Subjects who agree to discontinue all agents used to treat AD from screening through the final follow-up visit.

7. Willingness to avoid pregnancy or fathering of children based on the criteria below:
 - a. Woman of nonchildbearing potential (surgically sterile with a hysterectomy and/or bilateral oophorectomy OR postmenopausal, defined by last menstrual period > 12 months before screening).
 - b. Woman of childbearing potential who has a negative serum pregnancy test at screening and a negative urine pregnancy test before the first dose on Day 1 and who agrees to take appropriate precautions to avoid pregnancy (with at least 99% certainty) from screening through safety follow-up. Permitted methods that are at least 99% effective in preventing pregnancy (see [Appendix A](#)) should be communicated to the subject and their understanding confirmed.
 - c. Man who agrees to take appropriate precautions to avoid fathering children (with at least 99% certainty) from screening through safety follow-up. Permitted methods that are at least 99% effective in preventing pregnancy (see [Appendix A](#)) should be communicated to the subject and their understanding confirmed.
8. Ability to comprehend and willingness to sign an informed consent form (ICF).

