4. INVESTIGATIONAL PLAN

4.1. Overall Study Design

This is a randomized, vehicle- and active (triamcinolone 0.1% cream)-controlled study in subjects with mild to moderate AD. The study is double-blinded for vehicle, INCB018424 doses, and active control. Approximately 300 subjects will be randomized 1:1:1:1:1:1 to INCB018424 1.5% BID, INCB018424 1.5% QD, INCB018424 0.5% QD, INCB018424 0.15% QD, vehicle BID, and active control (triamcinolone 0.1% cream BID) and stratified by EASI score (≤ 7 and > 7). Subjects receiving QD regimens will apply vehicle at the evening application. Subjects will receive blinded study drug for 8 weeks. Subjects randomized to QD regimens will apply vehicle for the evening application. Subjects randomized to triamcinolone will apply triamcinolone 0.1% cream BID for 4 weeks and vehicle cream for 4 weeks to not exceed the allowable triamcinolone application duration ([Figure 2](#)).

At Week 8, subjects who meet criteria (compliant with the Protocol and no safety concerns) will be offered open-label treatment with INCB018424 1.5% cream BID for 4 weeks.

Through Week 8, subjects should continue to treat areas identified for treatment at baseline even if the area begins to improve. After Week 8, areas which were treated before Week 8 that are no longer symptomatic are not required to be treated.

Subjects will have follow-up assessments 1 month after the last application of study drug.

Study drug (INCB018424 cream, vehicle, or triamcinolone) may not be applied to the face or intertriginous areas. The face and intertriginous areas may be treated with hydrocortisone 2.5% cream during the study. Assessments of BSA should be based on treated areas (excluding the face and intertriginous areas that cannot be treated with study drug).

Subjects who develop additional areas of AD after the initiation of treatment may treat these additional areas (except the face and intertriginous areas) as long as the total treated BSA does not exceed 20% and there are no safety concerns regarding the additional application of study drug.

Subjects may continue to use bland emollients that do not contain urea or ceramides during the study. If bland emollients are used, the type of cream and amount of application should remain consistent for the duration of the study.

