6. STUDY ASSESSMENTS

All study assessments will be performed as indicated in the schedule of assessments ([Table 2](#)), and all laboratory assessments will be performed as indicated in [Table 3](#).

Table 2: Schedule of Assessments

Evaluation	Protocol Section	Screening		Treatment					EOT	Follow-Up 30 ± 7 Days After Last Dose
		Day -28 to -1	Baseline Day 1	Week 2 Day 14 ± 3 Days	Week 4 Day 28 ± 3 Days	Week 8 Day 56 ± 7 Days	Week 10 Day 70 ± 3 Days	Week 12 Day 84 ± 7 Days		
Administrative procedures										
Informed consent	7.1	X								
Contact IRT	7.2	X	X	X	X	X	X	X	X	X
Inclusion/exclusion criteria	3	X	X							
Demography and medical history	7.3	X								
Prior/concomitant medications	7.4	X	X	X	X	X	X	X	X	X
Dispense study drug and diary card	7.10.1		X	X	X	X	X			
Apply study drug	5.2		X	X	X	X	X			
Collect study drug tubes and review diary cards	7.10.1			X	X	X	X	X	X	
Assess compliance	5.3			X	X	X	X	X	X	
Safety procedures/assessments										
Comprehensive physical examination (height and weight at screening only)	7.5.2.1	X								X
Targeted physical examination	7.5.2.2		X	X	X	X	X	X	X	X
Vital signs	7.5.3	X	X	X	X	X	X	X	X	X
Hematology and chemistry assessments	7.5.5	X	X	X	X	X	X	X	X	
Free T4 and thyroid stimulating hormone		X								
Urinalysis	7.5.5.3	X								
Pregnancy test ^a	7.5.5.4	X	X	X	X	X	X	X	X	X
Serology	7.5.5.5	X								
12-lead ECG	7.5.4	X								
Assess AEs	7.5.1	X	X	X	X	X	X	X	X	X
Efficacy assessments										
EASI scoring	7.6.1	X	X	X	X	X	X	X	X	X
BSA treated w/study drug (4 regions and overall)	7.6.5	X	X	X	X	X	X	X	X	X
IGA	7.6.2	X	X	X	X	X	X	X	X	X
Photography	7.6.6		X		X					
Itch Numerical Rating Scale	7.6.4	Diary is completed each evening from screening through the last dose of study drug.								

^a All women will have a serum pregnancy test conducted at the screening visit and urine pregnancy tests conducted at all other visits (including baseline).

Table 3: Clinical Laboratory Assessments

Serum Chemistries	Hematology
Albumin	Hematocrit
Alkaline phosphatase	Hemoglobin
ALT	Mean corpuscular volume
AST	Platelet count
Bicarbonate	Red blood cell count
Blood urea nitrogen	Reticulocyte count
Calcium	White blood cell count
Chloride	White blood cell differential (5 part):
Creatinine	
 • Basophils • Eosinophils • Lymphocytes • Monocytes • Neutrophils
Glucose	
Lactate dehydrogenase	
Phosphorus	
Potassium	
Sodium	
Total bilirubin	
Total serum protein	
Other	Serology
Urinalysis	Hepatitis B surface antigen

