9.2. Selection of Sample Size

The assumptions in [Table 5](#) were used for the percentage change from baseline in EASI scores at Week 4.

Table 5: Assumed Percentage Change From Baseline in EASI at Week 4

Treatment	Percentage Change
Vehicle	30%
Triamcinolone 0.1% (active control)	50%
INCB018424 1.5% BID	75%
INCB018424 1.5% QD	65%
INCB018424 0.5% QD	50%
INCB018424 0.15% QD	30%

The standard deviation was assumed to be 0.13 (13%). These assumptions were based on the review of a historical clinical study in AD ([Beck et al 2014](#)).

In order to provide a large safety database and to provided adequate power for efficacy variables, the total sample size for the study is 300 subjects randomized in a 1:1:1:1:1:1 ratio (stratified by baseline EASI score) to INCB018424 1.5% BID, INCB018424 1.5% QD, INCB018424 0.5% QD, INCB018424 0.15% QD, triamcinolone (active control), and vehicle.

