3.2.2. Secondary Analysis

3.2.2.1. Tests in Branch 1

- **Step 1:** The first alternative hypothesis (noninferiority of INCB018424 1.5% BID compared with triamcinolone) will be tested at a 2-sided $\alpha = 0.03$ level if the primary test is significant. If the first alternative hypothesis is established, then hypotheses in Step 2 will be tested at an overall error rate of 0.03.
- **Step 2:** If Step 1 is established, then a superiority test of INCB018424 1.5% BID compared with triamcinolone and noninferiority test of INCB018424 1.5% QD compared with triamcinolone will be carried out using the Bonferroni-Holm procedure at an overall 2-sided $\alpha = 0.03$ level.
- **Step 3:** If both of the null hypotheses in Step 2 are rejected, then a superiority test of INCB018424 1.5% QD compared with triamcinolone will be carried out at a 2-sided $\alpha = 0.03$ level.

If all 4 tests in Branch 1 are significant, then the overall level ($\alpha = 0.03$) of Branch 1 will be reallocated to Branch 2, and the first alternative hypothesis in Branch 2 will be tested with start level of 2-sided 0.05. If 1 or more of the tests in Branch 1 is nonsignificant, there will be no level reallocated from Branch 1 to Branch 2, and the first alternative hypothesis in Branch 2 will be tested with start level of 2-sided $\alpha = 0.02$.

3.2.2.2. Tests in Branch 2

- Alternative hypotheses (superiority of INCB018424 1.5% QD and 0.5% QD compared with vehicle) will be tested in sequence using the alpha level decided in previous steps.

If 1 or more of the 4 tests in Branch 1 is nonsignificant, but all tests in Branch 2 are significant, then the alpha level will be reallocated to Branch 1, and Branch 1 will reopen with a start level of 2-sided $\alpha = 0.05$.

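### Does counting head and neck in EASI, when study drug is barred from the face, undermine the comparison with triamcinolone?

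*SAP*

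**What the plan says.** SAP 7.2.1 and Protocol Appendix B define total EASI as the sum of four regional scores with weights "Head/Neck (H) = 0.1, Upper limbs (UL) = 0.2, Trunk (T) = 0.3, and Lower limbs (LL) = 0.4". SAP 7.3.1 (primary) and 7.4.1 (key secondary) analyse percentage change from baseline in that total at Week 4. SAP 3.2.3 and 7.4.1 set the noninferiority margin against triamcinolone at -10% on the same measure.

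Protocol 4.1 restricts where the creams go: "Study drug (INCB018424 cream, vehicle, or triamcinolone) may not be applied to the face or intertriginous areas". It adds: "The face and intertriginous areas may be treated with hydrocortisone 2.5% cream during the study". Body surface area is limited accordingly; Protocol 3.1 admits "Subjects with BSA of AD involvement, excluding the face and intertriginous areas, of 3% to 20% at screening and baseline", and Protocol 4.1 bases later BSA assessments on treated areas.

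SAP 7.3.2 prespecifies a subgroup by baseline facial involvement. SAP Appendix A gives it tables for EASI (2.1.1.5), EASI response (2.1.2.3) and IGA response (2.1.3.3). The visible sensitivity analyses in SAP 7.3.3 are a last-observation-carried-forward ANOVA, the per-protocol population and possible missing-not-at-random models. None restricts the body regions.

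**The concern.** BSA leaves out the skin that cannot be treated, while EASI keeps it, which looks like a mismatch between treatment and endpoint. The 0.1 weight does not settle the matter, because the endpoint is a percentage of each subject's own baseline. A head/neck severity sum of 4 with area score 2 contributes 4 × 2 × 0.1 = 0.8 points. That is 11% of an EASI of 7 and 20% of an EASI of 4, and the trial enrols mild disease with a stratum at EASI ≤ 7.

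If barred skin responds alike in all arms, it draws the arms together. For superiority this costs a little power. For noninferiority with a fixed margin it could let a cream that is worse on treated skin pass, and comparison with triamcinolone is the key secondary objective.

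**Working it through.** **Inputs.** About 50 subjects per arm (SAP 3); SD 13 points and Table 5 means of 30% vehicle, 50% triamcinolone, 75% for 1.5% BID and 65% for 1.5% QD (Protocol 9.2); margin -10 (SAP 7.4.1); Step 1 at 2-sided 0.03 (SAP 3.2.2.1). The untreated share f of baseline EASI is not in the documents; 10% and 20% are assumptions. SDs of 20 and 30 are also assumptions.

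**The plan's own figures.** SE = 13 × √(2/50) = 2.6. Power above 99% against vehicle reproduces for differences of 45, 35 and 20 points (each > 99.9%). Noninferiority power at a true difference of zero, stated as above 99%, comes to 97.0% (normal) or 96.8% (t) with a 95% CI. That is a separate sample-size matter and does not depend on head and neck.

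**Dilution.** If barred skin responds equally in all arms, and the share is unrelated to response, then total-EASI difference = (1 − f) × treated-skin difference. The margin on the treated-skin scale is 10/(1 − f): 11.1 at f = 10%, 12.5 at f = 20%.

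**Error rate under a treated-skin null.** For a true treated-skin deficit of exactly 10, P(noninferior) = Φ(10f/SE − 2.170):

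| SD | SE | f = 0 | f = 10% | f = 20% |
|---|---|---|---|---|
| 13 | 2.6 | 1.5% | 3.7% | 8.1% |
| 20 | 4.0 | 1.5% | 2.7% | 4.7% |
| 30 | 6.0 | 1.5% | 2.3% | 3.3% |

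These rates belong to a null that the plan never sets. Its null is -10 on total EASI, where the Step 1 error is 1.5% at every f.

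**Margin against the control effect.** Table 5 is headed as percentage change in EASI, so triamcinolone minus vehicle is 50 − 30 = 20 points on the total. On treated skin that is 20/(1 − f). The margin is then 10/20, 11.1/22.2 or 12.5/25, which is 50% each time. Margin and control effect scale together.

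**Superiority to triamcinolone.** As headed, Table 5 gives +25 (BID) and +15 (QD) on total EASI, with nothing to dilute. Suppose instead that these are treated-skin differences and f = 20%: they become +20 and +12. After Step 1, "hypotheses in Step 2 will be tested at an overall error rate of 0.03"; that step covers BID superiority and QD noninferiority by Bonferroni-Holm, so BID superiority may face 0.03/2 = 0.015. Its power is > 99.9% at SD 13 and 99% at SD 20. QD superiority comes in Step 3 at 0.03, where power is 99.2% at SD 13 and 78.6% at SD 20. The level 0.015 does not apply to it.

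**What a rerun without head and neck would remove.** If a part h of f is head and neck, the remaining share is (f − h)/(1 − h). With half of f there (assumed):

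- f = 20%, h = 10%: remaining share 11.1%, implied margin 11.25 instead of 12.5, a change of 1.25 points.
- f = 10%, h = 5%: remaining share 5.3%, implied margin 10.56 instead of 11.11, a change of about 0.6 points.

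The 95% CI half-width for an arm difference is 5.2 points at SD 13 and 7.9 at SD 20.

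**The case for a change.** The best case for acting is that the analysis costs almost nothing. Regions are scored separately, so it needs one derived variable and one model rerun, and it is best fixed before sponsor staff see unblinded interim results. The facial-involvement subgroup keeps total EASI and splits the arms: if half the subjects have no facial disease (assumed), 25 per arm gives about 78% noninferiority power with a 95% CI. Hydrocortisone use might also differ by arm.

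The facts and the low cost stand. The benefit is weaker:

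- Such a rerun would carry no alpha and no margin, so no conclusion could turn on it.
- It is a poor stand-in for treated skin. Only the face and intertriginous areas are barred, so dropping head and neck discards skin that may be treated, such as the neck outside its folds, and keeps barred intertriginous skin on trunk and limbs.
- It is undefined for a subject with no baseline disease in the other three regions and unstable when that baseline is very small.

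One condition also stands. The constant 50% relies on reading Table 5 as total EASI. If its 20-point control effect were a treated-skin figure, the share would be 11.1/20 = 56% or 12.5/20 = 62.5%. Nothing in Protocol 9.2 suggests that reading, and a rerun without a margin would not alter it.

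**Conclusion.** The concern does not hold. Head and neck do count, and no visible analysis leaves them out, but the plan tests what it says it tests: percentage change in total EASI, against a margin defined on that score. At that null the error is as planned, superiority is at most conservative, and the margin stays at 50% of the Table 5 control effect for any untreated share. The shift to -11.1 or -12.5 concerns treated skin alone, about which the plan draws no noninferiority conclusion.

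This rests on an equal response of barred skin across arms and on Table 5 meaning total EASI, as it is headed. The untreated share is unknown. Part of SAP section 7 is blacked out, so a related analysis may exist there; the conclusion does not need one. A report of noninferiority should be worded for total EASI, as SAP 7.4.1 already does.
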